## Simulation distribution

*Discrete distribution used for simulations based on the distribution observed in the Above Bifurcation group in Monahan, et al.*

If the test for Hypothesis 1 concludes noninferiority (scenario A, B, or C in Figure 1), we will test for a difference in overall duration of administration again using the Wilcoxon-Mann-Whitney test.

Power is approximated by a two-sample t-test calculation. Assuming a standard deviation of SD=37 hours (corresponding to an interquartile range of 50 to 100 hours), we expect that a sample size of ***n=35*** provides 80% power to detect a mean group difference of 25 hours with a two-sided alpha of 5%.

**Total enrollment:** ***70 subjects*** plus 30 for misplaced catheters or subjects otherwise unable to be randomized; and subjects who withdraw for both infraclavicular and popliteal-sciatic groups. This allows for a possible total of 200 subjects total.

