#### **Postoperative Procedures:**

*SOC (mandated for study purposes):* Following completion of the procedure in the operating room, an infusion pump (Infutronix, Natick, Massachusetts) with a 500 mL ropivacaine 0.2% reservoir will be attached to the perineural catheter. For patients in the **continuous infusion** group, the pump will provide an 8 (infraclavicular) or 6 (sciatic) mL/h basal infusion and a 4 mL patient-controlled bolus with a 30-minute lockout (standard at UCSD).

*Experimental:* For patients in the **titratable automated intermittent bolus** group, the pump will provide an automatic 11 (infraclavicular) or 8 (sciatic) mL bolus once every 2 hours and have a 4 mL patient-controlled bolus with a 30 minute lockout. In addition, for those in the **titratable automated intermittent bolus** group, the infusion pump will be set in a “pause” mode that delays initiation of the automated bolus doses by 5 hours (this can be over-ridden by patients if they would like to initiate their perineural infusion earlier than 5 hours). Lastly, subjects in the **titratable automated intermittent bolus** group will be able to titrate the volume of their automated bolus up or down within the range of 1-16 mL.

*Per standard of care,* the pump will not administer more than 20 mL during each hour (below the current UCSD maximum). Prior to discharge, the functioning of the infusion pump will be explained, so that they understand that they should push the bolus button if they have pain. This is accurate regardless of which treatment group the patient is randomized to, ensuring that all subjects will receive adequate analgesia.

*Experimental:* Subjects will be contacted via phone for the 9 days following surgery to collect information regarding surgical pain (Numeric Rating Scale of 0 to 10, with “0” being no pain and “10” being the worst pain ever experienced), analgesic use, sleep disturbances, infusion side effects, and satisfaction with pain control. When 500 mL has been infused or on Day 8—whichever comes first—subjects will remove the catheter and

place the pump in a pre-addressed and -stamped package for return [note that it is standard of care for patients to remove the catheters at home; but, listed as experimental here due to the timing of catheter removal which will be later than is standard of care due to the experimental local anesthetic administration protocol].

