**Data Acquisition [all experimental]:**

Data will be gathered from the patients' electronic medical record, by telephone follow-up, and from the memory of each infusion pump. Subjects will be contacted by phone for the 9 days following surgery. Data will be recorded on paper Case Report Forms, including: patient name, medical record number, age, sex, height, weight, surgical procedure, date of procedure, anesthesiology attending overseeing/placing catheter, randomization number, whether a femoral/saphenous block was placed, if the catheter was placed per protocol, if the block set up successfully, intraoperative fentanyl, morphine and dilaudid, and the time of infusion initiation.

**Outcomes (End Points):** For the first 9 postoperative days, subjects will be asked to answer the questions with regard to the previous 24 hours: opioid consumption, worst pain, average pain, least pain, current pain (Numeric Rating Scale for all pain scores), any numbness on extremity (scale 0=absent to 10=insensate), fluid leakage (yes/no), number of sleep disturbances due to pain (awakenings), satisfaction with analgesia (0=very dissatisfied, 10=very satisfied), the bolus volume for subjects in the titration group, and the seven questions of the Brief Pain Inventory's Interference Scale. The date and time of infusion completion will be recorded as will the reason for catheter removal (reservoir exhaustion vs. another reason).

**Statistics:** The infraclavicular and popliteal-sciatic groups will be analyzed separately as two distinct analyses. This study will be powered for two primary end points: (1) the average NRS queried on postoperative day 1; and (2) the duration of treatment from when the infusion pump was initially turned on until the local anesthetic reservoir was exhausted [recorded by the infusion pump memory]. The dual hypotheses will be tested with a serial testing strategy, such that Hypothesis 2 will not be formally tested unless the conclusion of Hypothesis 1 is at least "noninferiority". Following the approach described in Althunian et al, noninferiority will be assessed by comparing the lower limit of the 95% confidence interval for the difference (CB minus AB) on the NRS (range: 0 to 10) to a pre-specified noninferiority margin of 1.7 NRS units (see Figure 1). This will provide evidence that the analgesia provided by the novel automated boluses is no worse than 1.7 NRS units compared to CB.

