**Sample size estimate:** Power is simulated based on the distribution of pain measured with the Numeric Rating Scale (NRS) observed in the "Above bifurcation" group in Monahan, et al. (*Anesth Analg* 2016;122:1689-95) for the sciatic catheter group. For the infraclavicular group, we simulated NRS scores from the basal/bolus treatment from [name] et al. (*Anesthesiology* 2004;100:395-402). Specifically, we simulate NRS scores from a discrete distribution as depicted in Figure 1, panel A (infraclavicular) and Figure 2 (sciatic). This results in an expected interquartile range of approximately 1 to 4, and a median of approximately 3 NRS units. We simulated 1000 trials in which the two groups, n=35 per group, were assumed to follow the same discrete distribution, submitted each trial to a Wilcoxon-Mann-Whitney test, and derived 95% confidence intervals (Bauer 1972; Hothorn, et al. 2008). Out of the 1000 trials, 792 (79.2%) correctly resulted in a conclusion of non-inferiority; suggesting that the probability that the trial correctly concludes non-inferiority is about 80% when the groups follow exactly equivalent distributions.

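### The duration power rests on an SD and IQR that the control arm cannot have when pumps run to exhaustion, and its 80% does not allow for the Hypothesis 1 gate

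*Combined protocol and SAP*

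**What the plan says.** All of this is in section 9 of the combined protocol and SAP.

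- **Claim (Statistics).** "This study will be powered for two primary end points": average NRS pain on postoperative day 1, and "the duration of treatment from when the infusion pump was initially turned on until the local anesthetic reservoir was exhausted". The infraclavicular and popliteal-sciatic groups are analysed separately.
- **Gate (Statistics).** Testing is serial, "such that Hypothesis 2 will not be formally tested unless the conclusion of Hypothesis 1 is at least" noninferiority.
- **Power for Hypothesis 1 (Sample size estimate).** Of 1000 simulated trials with n=35 per group, "792 (79.2%) correctly resulted in a conclusion of non-inferiority". The text concludes that this probability "is about 80% when the groups follow exactly equivalent distributions".
- **Power for Hypothesis 2 (end of the sample size text).** "Assuming a standard deviation of SD=37 hours (corresponding to an interquartile range of 50 to 100 hours"), n=35 "provides 80% power to detect a mean group difference of 25 hours with a two-sided alpha of 5"%. The figure comes from a two-sample t-test approximation; the planned test is Wilcoxon-Mann-Whitney.
- **Control pump programme (Postoperative Procedures).** With a 500 mL reservoir, "the pump will provide an 8 (infraclavicular) or 6 (sciatic) mL/h basal infusion and a 4 mL patient-controlled bolus with a 30-minute lockout". The 5-hour pause and the adjustable bolus volume are described only for the titratable group.

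**The concern.** There are two separate problems, and they do not push power in the same direction.

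**Planning SD.** The control arm has a fixed basal rate and a fixed reservoir, so its exhaustion time has a hard upper limit. Patient boluses can only shorten the run. An SD of 37 h tied to quartiles of 50 h and 100 h does not look compatible with that limit, and one SD serves two sites whose control rates differ.

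**Gate.** The 80% for duration takes no account of the chance that Hypothesis 1 fails and duration is never formally tested. A reader told that the study is powered for two primary end points could take 80% as the chance of a positive duration result.

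Longer treatment is the main reason given for the trial in sections 5 and 7. The risk of not being able to claim it should be visible, and the power should be checkable at each site.

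**Working it through.** **1. Reproduce the stated figure.** Inputs: difference 25 h, SD 37 h, n=35 per group, two-sided alpha 5%.

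- IQR to SD under normality: 50 / (2 × 0.6745) = 37.1 h, so SD and IQR agree with each other.
- Noncentrality: 25 / (37 × √(2/35)) = 2.83. With 68 degrees of freedom the exact t-test power is **79.6%** (normal approximation 80.7%).

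The 80% is therefore right for the duration test taken alone.

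**2. Limits on control duration when the pump runs to exhaustion.** Inputs: 500 mL, basal 8 or 6 mL/h, and at most two 4 mL boluses per hour under the 30-minute lockout (8 mL/h). The largest possible SD of a bounded variable is half its range.

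| | Infraclavicular | Sciatic |
|---|---|---|
| Longest run | 500/8 = 62.5 h | 500/6 = 83.3 h |
| Shortest run | 500/(8+8) = 31.3 h | 500/(6+8) = 35.7 h |
| Largest control SD | (62.5 − 31.3)/2 = 15.6 h | (83.3 − 35.7)/2 = 23.8 h |

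Using the plan's 20 mL/h hourly limit instead of the lockout gives a shortest run of 25 h and SD ceilings of 18.75 h and 29.2 h. The conclusion is the same.

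If catheters removed early counted as durations from 0 h, the ceilings would be 62.5/2 = 31.3 h and 83.3/2 = 41.7 h. Then 37 h stays out of reach for infraclavicular and is possible for sciatic only with an extreme two-cluster distribution. The 100 h upper quartile remains impossible in the control arm at both sites.

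**3. What the experimental SD must be.** With equal groups the t-test depends on the root-mean-square of the two SDs. For that to be 37 h with control at its ceiling:

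- Infraclavicular: √(2 × 37² − 15.6²) = 49.9 h
- Sciatic: √(2 × 37² − 23.8²) = 46.6 h

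A smaller control SD requires a larger experimental SD.

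**4. Stand-alone power at 25 h, control SD at its ceiling** (unequal-variance t-test, n=35 per arm). The documents give no experimental SD, so two assumed values are shown:

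| Experimental SD | Infraclavicular | Sciatic |
|---|---|---|
| 37 h | 95% | 91% |
| 50 h | 79% | 74% |

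**5. Power after the gate, on the plan's own inputs.** Hypothesis 1 is 0.792 and Hypothesis 2 is 0.796.

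- Independent results: 0.792 × 0.796 = **0.630**
- No dependence assumption: from 0.792 + 0.796 − 1 = **0.588** to min(0.792, 0.796) = **0.792**
- Bivariate normal correlation of 0.3, 0.5 and 0.7: 0.657, 0.679 and 0.705
- Correlation of −0.3 and −0.7: about 0.61 and 0.59

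**The case against.** The case on the other side has real force in places.

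- **No sum is wrong.** The 80% and the SD-to-IQR conversion both reproduce. This stands: the fault lies in the inputs and in what is left unreported.
- **The plan never assigns the SD or IQR to the control arm.** A single SD can be read as a root-mean-square value, and the IQR might describe both arms pooled. The first reading is possible, but only with an experimental SD near 50 h that is stated nowhere. The second does not help, because a two-sample t-test needs within-arm spread and a pooled IQR also contains the treatment difference.
- **The SD point shows no harm.** At an experimental SD of 37 h, power rises. This stands, and no claim of low power is made on that ground. The point is that the power may fall on either side of 80% and the reader cannot tell which.
- **The 25 h difference may be pessimistic.** With default bolus volumes, no patient boluses and no titration, the programme implies 500/5.5 + 5 − 62.5 = 33 h (infraclavicular) and 500/4 + 5 − 83.3 = 47 h (sciatic). With control SD at its ceiling and experimental SD 50 h, stand-alone power is about 96% and 99.8%. Under independence it is about 76% and 79% after the gate. Titration and boluses could move these differences either way, and even here the figures stay below 80%.
- **The gate is disclosed.** The duration paragraph opens with the condition that Hypothesis 1 has succeeded, so the 80% can be read as power once the gate is passed. That reading is fair. It still leaves the power of the sequence unreported.

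**Conclusion.** Both parts hold.

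For pumps run to exhaustion, the control arm cannot have an SD of 37 h or an upper quartile of 100 h at either site. A common SD of 37 h survives only as an average that relies on an unstated experimental SD of at least about 50 h (infraclavicular) or 47 h (sciatic). This makes the duration power uncheckable by site; it does not by itself show that the trial is underpowered.

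On the plan's inputs, the chance of passing the gate and then showing a duration difference is about 63% under independence and 59% to 79% in general. It comes close to 80% only if the two results are almost fully dependent. These figures apply to each site separately, at a 25 h difference and with equal pain distributions. If the experimental arm has less pain, the gate is more likely to be passed and the figures improve. The plan should be corrected on both counts, but neither invalidates the design.

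**What to change.** Rewrite the Hypothesis 2 power paragraph as follows:

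1. Give the power separately for infraclavicular and sciatic catheters, with an SD for each arm. The control SD should fit exhaustion times of at most 62.5 h or 83.3 h. State the experimental SD assumed and its basis.
2. Label the 80% as the power of the duration test alone.
3. Add the power after the Hypothesis 1 gate, with the dependence assumption and the range. On the current inputs this is about 63% under independence and 59% to 79% overall, when pain distributions are equal.

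Sample size, test, margin, gate and pump programme all stay as they are. The cost is one paragraph and a less favourable stated power for the dual claim.

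### The 80% power for duration ignores the serial gate: at the plan's own inputs the chance of a formal duration result is about 63% if the two tests are independent

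*Combined protocol and SAP*

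**What the plan says.** The Statistics paragraph of Section 9 states that "This study will be powered for two primary end points": average NRS pain on postoperative day 1 (Hypothesis 1, noninferiority with a margin of 1.7 NRS units) and duration of treatment (Hypothesis 2). The two are tested in series: "Hypothesis 2 will not be formally tested unless the conclusion of Hypothesis 1 is at least" noninferiority. The duration paragraph repeats the condition, opening with "If the test for Hypothesis 1 concludes noninferiority".

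Power is given for each step separately.

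- **Hypothesis 1.** Of 1000 simulated trials with 35 per group, "792 (79.2%) correctly resulted in a conclusion of non-inferiority". The text adds that the probability "is about 80% when the groups follow exactly equivalent distributions".
- **Hypothesis 2.** From a two-sample t-test approximation with SD 37 hours, the sample size "provides 80% power to detect a mean group difference of 25 hours with a two-sided alpha of 5" percent.

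On the two catheter sites, the plan says: "The infraclavicular and popliteal-sciatic groups will be analyzed separately as two distinct analyses". The sample size paragraph names a different source study for each site but reports a single simulation result. The caption that survives in the text reads "Discrete distribution used for simulations based on the distribution observed in the Above Bifurcation group", which is the source named for the sciatic cohort.

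**The concern.** Under the serial rule, a formal duration result requires two events: noninferiority on pain, then significance on duration. That pair is also what the two-part hypothesis in Section 6 needs in order to succeed. The plan reports a probability near 80% for each step and none for the pair. A reader who is told that the study is powered for both end points, and who then sees two figures near 80%, would reasonably take 80% as the chance of showing a longer duration. The serial order protects the type I error rate, but it has a power cost that the plan does not show.

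The cohort gap adds to this. Each cohort has its own gate, so each has its own joint probability. With one unattributed Hypothesis 1 figure, the joint probability for the other cohort cannot be computed from the plan.

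**Working it through.** **Inputs, all from Section 9.** 35 per group; 1:1 allocation; duration difference 25 h; SD 37 h; two-sided 5%; margin 1.7 NRS units; probability of passing Hypothesis 1 = 0.792 at zero true pain difference.

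**1. Reproduce the plan's figure.** The SD follows from the stated quartiles of 50 and 100 h: 50/1.349 = 37.1 h. The standardised difference is 25/37 = 0.676, and the noncentrality is 0.676 × √(35/2) = 2.83. The noncentral t distribution gives power 0.796; the normal approximation gives 0.807. The stated 80% is correct as stand-alone power.

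**2. Apply the gate.** Under independence:

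P(pass H1 and win H2) = 0.792 × 0.796 = 0.630.

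With the plan's rounded 80% it is 0.792 × 0.80 = 0.634.

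**3. Relax independence.** With a bivariate normal model for the two test statistics and marginals 0.792 and 0.796:

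| Correlation | Joint probability |
|---|---|
| −0.5 | 0.597 |
| −0.3 | 0.608 |
| 0 | 0.630 |
| +0.3 | 0.657 |
| +0.5 | 0.679 |

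The bounds under any dependence are 0.792 + 0.796 − 1 = 0.588 and min(0.792, 0.796) = 0.792. The upper bound becomes 0.80 only if both marginals are rounded to 80%.

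**4. Simulation error in the gate.** 792 of 1000 has a 95% interval of 0.766 to 0.816. Multiplied by 0.796, this gives 0.61 to 0.65.

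**5. The planned test.** Duration will be compared by the Wilcoxon-Mann-Whitney test. On normal data with relative efficiency 3/π, its stand-alone power is 0.777, and the joint figure under independence is 0.792 × 0.777 = 0.615.

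**6. Non-zero true pain difference.** I assume a normal statistic calibrated to the plan's 79.2%: SE = 1.7/(0.813 + 1.96) = 0.613. With d the bolus arm's advantage, the gate is Φ((1.7 + d)/0.613 − 1.96). Tests are taken as independent.

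| d (NRS units) | Gate | Joint |
|---|---|---|
| −0.5 | 0.499 | 0.397 |
| −0.25 | 0.657 | 0.523 |
| 0 | 0.792 | 0.630 |
| +0.25 | 0.889 | 0.707 |
| +0.5 | 0.948 | 0.755 |

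**7. Larger duration difference.** This uses the starting pump settings in Postoperative Procedures, a 500 mL reservoir, no patient boluses and no titration, with SD 37 h, zero pain difference and independence.

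- Infraclavicular: 500/(11/2) − 500/8 = 90.9 − 62.5 = 28.4 h; power 0.886; joint 0.702.
- Sciatic: 500/(8/2) − 500/6 = 125.0 − 83.3 = 41.7 h; power 0.996; joint 0.789.
- If the 5-hour pause counts as treatment time: 33.4 h gives 0.761, and 46.7 h gives 0.792.

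These are illustrations, not forecasts, because patients may bolus and titrate.

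The 79.2% is taken as reported. The plotted distribution behind it is not in the text available to me, so I could not reproduce it exactly.

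**The case against.** The strongest reply is that nothing is miscalculated or hidden. The gate, the 79.2% with its condition, and the 80% are all on the page. The duration paragraph begins with the gate, so the 80% can be read as power once the test is reached. Noninferiority alone is a formal conclusion, so 63% is not the chance that the trial yields any primary result. The 25 h is a difference to detect rather than the expected effect, and at the starting pump settings the joint figure is 70% to 79%.

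Most of this is true, and it makes the point an omission rather than an arithmetic error. It does not supply the missing number. If the 80% is read as conditional on reaching the test, the unconditional probability is still 0.792 × 0.80 = 63%. The 25 h is the plan's own design value, so it is the right place to state the gated figure. A larger duration gain cannot lift that figure above the gate's 79.2% at zero pain difference.

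The sign of the dependence is also open. Patients are told to bolus for pain, so more pain may go with shorter duration; that would make the link positive and the range 63% to 68%. But heavier dosing could also mean less pain and an earlier empty reservoir. The documents do not settle this, so the full bounds should stand beside the independence figure.

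On the cohorts, figures are missing from the text I have, so the single caption is weak evidence by itself. The prose still reports one result for two named source distributions.

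**Conclusion.** The concern holds. The 80% is correct as stand-alone power, but the gated design does not deliver 80% for a formal duration result at the plan's own inputs. With a 25 h difference and zero true pain difference the probability is about 63% under independence, 60% to 68% for correlations of −0.5 to +0.5, and 59% to about 79–80% under any dependence. It depends on the true pain difference (40% at 0.5 NRS units worse, 75% at 0.5 better) and rises with a larger duration effect. These figures apply to a cohort only if its gate probability is 79.2%; for at least one cohort the plan does not show that it is.

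**What to change.** Revise the sample size text in Section 9.

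- Label the 80% as ungated (marginal) power for duration.
- Add the probability of passing Hypothesis 1 and then winning Hypothesis 2: on the stated inputs about 63% under independence, with bounds of 59% and about 79–80%. State the dependence assumption and the zero-pain-difference condition beside it.
- Say which cohort the 79.2% describes, report the Hypothesis 1 result for the other, and compute the gated figure for each cohort from its own simulation.
- Ideally, simulate pain and duration together in each cohort, apply the planned Wilcoxon-Mann-Whitney procedures, and show one or two non-zero pain differences.

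The cost is a revised paragraph and, ideally, one joint simulation per cohort. Sample size, tests and margin stay as they are. The only drawback is a less favourable stated figure.

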### 10. HUMAN SUBJECTS

**Inclusion criteria:** (1) patients undergoing ulnar and/or radial fracture open reduction internal fixation or painful foot and/or ankle surgery with a planned infraclavicular or popliteal sciatic perineural catheter, respectively, for postoperative analgesia; and (2) age 18 years or older.

**Exclusion criteria:** (1) Daily opioid use within the previous 4 weeks; (2) clinical neuro-muscular deficit of either the brachial plexus (infraclavicular) or sciatic nerve (sciatic catheters) and its branches and/or innervating muscles; (3) morbid obesity [body mass index  $> 35 \text{ kg/m}^2$ ]; surgery outside of the ipsilateral sciatic and saphenous nerve distributions for sciatic catheters [e.g., iliac crest bone graft]; (5) pregnancy [as determined by

a urine pregnancy test prior to any study interventions]; and (6) incarceration.

